2.4 Study Treatment

Subjects in the Adult Cohort were scheduled to be treated with 5 mg palovarotene daily for up to 24 months (non-flare-up based treatment); however, some adult subjects chose not to receive non-flare-up based treatment.

Flare-up based treatment will begin as soon as possible after a subject reports onset of a flare-up and the flare-up has been confirmed by the Investigator. In the event of an eligible flare-up, subjects in the Adult Cohort will receive open-label palovarotene treatment as follows:

- 20 mg for 28 days. The first dose will be taken upon flare-up confirmation by the Investigator.
- 10 mg for 56 days, for a total flare-up treatment duration of 84 days; treatment may be extended if the flare-up is ongoing and continue until the flare-up resolves. Dosing will be extended in 4-week intervals and be based on clinical signs and symptoms as assessed by the Investigator.

Subjects not receiving non-flare-up based dosing will only be treated during eligible flare-ups and will receive weight-adjusted doses of 20 and 10 mg palovarotene as follows:

Weight Range Category	20-mg Equivalent	15-mg Equivalent	10-mg Equivalent	7.5-mg Equivalent*	5-mg Equivalent*
20 to <40 kg	12.5 mg	10 mg	6 mg	4 mg	3 mg
40 to <60 kg	15 mg	12.5 mg	7.5 mg	5 mg	4 mg
≥60 kg	20 mg	15 mg	10 mg	7.5 mg	5 mg

* In the event of dose de-escalation.

If the subject experiences intolerable side effects during flare-up based dosing, the dose may be reduced to the next lower dose; if the subject is already receiving the lowest possible dose, then study drug will be discontinued. Treatment may be extended after the 84-day treatment period (flare-up based dosing) if the flare-up is ongoing and continue until the flare-up resolves. Dosing will be extended in 4-week intervals based on clinical signs and symptoms as assessed by the Investigator, with remote visits performed every 2 weeks while on treatment. In the event the subject requires dose de-escalation due to an intolerable side effect for a previous flare-up, then the dose the subject will receive for a subsequent flare-up will be determined by the Investigator and the Medical Monitor.

After the Flare-up Day 84/EOT visit has been conducted and the flare-up is considered resolved, subjects in the Adult Cohort will resume the non-flare-up based treatment.

Subjects not receiving non-flare-up based dosing who do not experience an eligible flare-up will not be treated.

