7.9 Columbia-Suicide Severity Rating Scale

Suicidal ideation and behavior will be assessed using the Columbia-Suicide Severity Rating Scale (C-SSRS).

Data listings will be provided for (1) all C-SSRS results; and (2) for subjects reporting any type 4 or type 5 suicidal ideations.

8 Pharmacokinetics Data

Pharmacokinetics will be assessed within 7 days of flare-up based treatment initiation and at the end of treatment for the first treated flare-up. Blood samples will be taken at 0, 3, 6, 10, and 24 hours post-dose.

Plasma palovarotene concentrations will be summarized with descriptive statistics (number of non-missing values, arithmetic mean, standard deviation, standard error, coefficient of variation, geometric mean, median, minimum, and maximum). All plasma concentrations below the limit of quantification (LOQ) will be set to zero for the purpose of calculating descriptive statistics. If

at any time point, 1/3 or more of subjects have <LOQ values, descriptive statistics will not be calculated at that time point. PK concentrations will be imputed using the following:

- If 0-hour concentration missing, then 24-hour concentration used to replace the missing concentration.
- If 24-hour concentration missing, then 0-hour concentration used to replace the missing concentration.
- Invalid 24-hour concentrations were replaced with the 0-hour concentrations. Twenty-four-hour concentrations were determined to be invalid if concentration is greater than the 10-hour value (i.e. assumed to have been obtained after next day dose instead of before next day dose).

If any other blood sample collections are missing, PK parameters will not be assessed. Actual sampling times will be used for the PK analysis, if available. Nominal sampling times will be used for descriptive statistics.

Individual concentration-time profiles for palovarotene will be presented (linear and semi-logarithmic scales). Arithmetic means (+/- standard deviation) concentration-time profiles will also be presented (linear and semi-logarithmic scales).

An exploration of the effects of body weight on PK will be performed as the data allow.

The PK analysis of palovarotene will be conducted using model-independent methods as implemented in WinNonlin™. The PK variables analyzed will include $AUC_{0-24(ss)}$, $C_{max(ss)}$, $C_{min(ss)}$, $T_{max(ss)}$, CL/F , λ_z , and $t_{1/2z}$ at steady-state. The PK variables are defined as follows:

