7.9.4.1 Assessments for Spinal Health

WBCT scan assessments described above, will also be used to analyze spinal bone mineral density, bone strength, bone mineral content and fractures, utilizing biomechanical computed tomography (BCT) analysis. Additionally descriptive statistics will be provided for each timepoint.

8 Pharmacokinetics Data

Pharmacokinetics of palovarotene dosing will be assessed twice during flare-up based treatment: once during the 20-mg regimen at any time between Study Days 4 to 28, and once during the 10-mg regimen at any time between Study Days 32 to 84, for the first treated flare-up only. If this is not possible for the first treated flare-up, PK blood samples can be obtained during any subsequent flare-up dosing cycle. Pharmacokinetic blood samples will be collected at pre-dose and 3, 6, 10, and 24 hours post-dose. Subjects who underwent PK assessment under PVO-1A-202 Protocol Amendment 3 will not have PK assessed again under PVO-1A-202 Amendment 4.

Blood samples for PK assessment of non-flare-up dosing will be collected at the first 3-month safety assessment at pre-dose and 3, 6, 10, and 24 hours post-dose; if samples cannot be or were not obtained at the 3-month safety assessment, or if a subject is on flare-up based treatment, then the PK blood sample for non-flare-up based treatment can be obtained during any subsequent 3-month safety visit.

The allowed time deviation windows for pre-dose blood sample is 1 hour before dosing. The concentrations outside the sampling window will be listed but not used for PK parameter calculation and summary statistics. Plasma palovarotene concentrations will be summarized with descriptive statistics (number of non-missing values, arithmetic mean, standard deviation, standard error, coefficient of variation, geometric mean, median, minimum, and maximum).

All plasma concentrations below the limit of quantification (LOQ) will be set to zero for the purpose of calculating descriptive statistics. If at any time point, 1/3 or more of subjects have <LOQ values, descriptive statistics will not be calculated at that time point. PK concentrations will be imputed using the following:

- If 0-hour concentration missing, then 24-hour concentration used to replace the missing concentration.
- If 24-hour concentration missing, then 0-hour concentration used to replace the missing concentration.

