- Invalid 24-hour concentrations replaced with the 0-hour concentrations. Twenty-four-hour concentrations are determined to be invalid if concentration is greater than the 10-hour value (i.e. assumed to have been obtained after next day dose instead of before next day dose).

For some subject who has both 0-hour and 24-hour concentration missing, the missing values will not be imputed. Data will be listed but excluded from PK parameter calculation.

If any other blood sample collections are missing, PK parameters will not be assessed. Actual sampling times will be used for the PK analysis, if available. Nominal sampling times will be used for descriptive statistics.

Individual concentration-time profiles for palovarotene will be presented (linear and semi-logarithmic scales). Arithmetic means (+/- standard deviation) concentration-time profiles will also be presented (linear and semi-logarithmic scales).

An exploration of the effects of body weight on PK will be performed as the data allows.

The PK analysis of palovarotene will be conducted using model-independent methods as implemented in WinNonlin™. The PK parameters analyzed will include $AUC_{0-24(ss)}$, $C_{max(ss)}$, $C_{min(ss)}$, $T_{max(ss)}$, $T_{min(ss)}$, CL_{ss}/F , λ_z , and $t_{1/2}$ at steady-state. The PK parameters are defined as follows in Table 8:

Table 8: PK Parameters

$AUC_{0-24(ss)}$	Area under the concentration versus time curve over the 24-hour dosing interval; calculated using linear trapezoid rule.
$C_{max(ss)}$	Maximum measured plasma concentration at steady-state.
$C_{min(ss)}$	Minimum measured plasma concentration at steady-state.
$T_{max(ss)}$	Time of maximum measured plasma concentration at steady-state, obtained by inspection.

$T_{\min(ss)}$	Time of minimum measured plasma concentration at steady-state, obtained by inspection.
CL_{ss}/F	Clearance defined as: Dose/AUC _{0-24(ss)} .
λ_z	Terminal rate constant
$t_{1/2}$	Apparent terminal elimination half-life; calculated as $\ln(2)/\lambda_z$. The number of data points included in the regression will be determined by visual inspection, but a minimum of three data points in the terminal phase, excluding C_{\max} , will be required to estimate λ_z .

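### The PK substitution rules do not settle the case of a missing 0-h and an invalid 24-h sample; run as listed, they put a presumed post-dose value at both ends of the profile

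*SAP*

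**What the plan says.** Part C SAP Section 8 sets five sampling times: "Pharmacokinetic blood samples will be collected at pre-dose and 3, 6, 10, and 24 hours post-dose". It then lists three substitutions as bullets:

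- For a missing 0-h sample: "If 0-hour concentration missing, then 24-hour concentration used to replace the missing concentration".
- The mirror rule covers a missing 24-h sample, which takes the 0-h value.
- An invalid 24-h value is replaced by the 0-h value. The test is "Twenty-four-hour concentrations are determined to be invalid if concentration is greater than the 10-hour value", and the stated presumption is that such a sample was drawn after the next day's dose.

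Part C adds an exclusion: "For some subject who has both 0-hour and 24-hour concentration missing, the missing values will not be imputed". Such data are listed but kept out of the parameter calculation.

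Part B SAP Section 8 gives the same three rules ("Invalid 24-hour concentrations were replaced with the 0-hour concentrations") without the exclusion sentence.

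Both sections use actual sampling times for the PK analysis if available, but the validity rule does not refer to them. AUC0-24 is by linear trapezoid, CL/F is dose divided by AUC0-24, and Cmin is the lowest measured concentration. Part C withholds lambda-z if Tmax is among the last three points, if the fitted slope is positive, or if the terminal phase looks non-linear. Part B requires only three terminal-phase points, excluding Cmax, with the number used chosen by visual inspection.

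**The concern.** The first rule does not require the 24-h value to be valid before it stands in for the 0-h value. The third does not require the 0-h value to have been observed before it replaces the 24-h value. When the 0-h sample is missing and the 24-h sample fails the test, each rule therefore points to the other.

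In the listed order, the suspect value moves to 0 h and is then copied back to 24 h. A value that the SAP itself believes to be post-dose then serves as both troughs. The 10-24 h trapezoid covers 14 of the 24 hours, so the 24-h value weighs heavily in AUC0-24 and hence in CL/F.

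Separately, because the test looks only at concentration, a post-dose sample that has not yet climbed above the 10-h value is accepted as a true trough.

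**Working it through.** The SAPs give no PK figure to reproduce. The check traces the rules and then sizes the result on an assumed profile.

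**Tracing the rules.** Let C0 be missing and the observed 24-h value be C\*, with C\* above C10.

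| Reading | 0 h | 24 h | Result |
|---|---|---|---|
| (a) Listed order | C\* | C\* | Suspect value at both ends |
| (b) All rules applied to the raw data at once | C\* | empty | Suspect value at one end; no 24-h point |
| (c) Validity first, invalid treated as missing | empty | empty | Part C excludes the profile; Part B is silent |

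The text fixes none of the three.

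**Trapezoid weights** (times 0, 3, 6, 10 and 24 h, from the SAP). C0 carries 3/2 = 1.5 h and C24 carries 14/2 = 7 h. If both true troughs equal T, reading (a) changes AUC by (1.5 + 7)(C\* − T) = 8.5(C\* − T).

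**Illustrative profile** (assumed, arbitrary units): 10, 100, 70, 40, 10.

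AUC = 3(10+100)/2 + 3(100+70)/2 + 4(70+40)/2 + 14(40+10)/2 = 165 + 255 + 220 + 350 = 990. Cmin = 10.

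Reading (a):

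| C\* | Added AUC | AUC | Change in AUC | Change in CL/F | Cmin |
|---|---|---|---|---|---|
| 50 | 8.5×40 = 340 | 1330 | +34% | 990/1330 − 1 = −26% | 40 |
| 80 | 8.5×70 = 595 | 1585 | +60% | 990/1585 − 1 = −38% | 40 |
| 100 | 8.5×90 = 765 | 1755 | +77% | 990/1755 − 1 = −44% | 40 |

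Cmin stops at 40, the 10-h value, because that is then the lowest concentration in the profile. No true trough is left.

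Reading (b): C\* = 50 adds 1.5×40 = 60 to the 0-10 h area (640 to 700, +9%), and AUC0-24 has no end point.

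**Sample that escapes the test.** A post-dose C24 of 35 is below C10 = 40 and passes. With C0 observed, AUC rises by 7×25 = 175 to 1165 (+18%). With C0 missing, it rises by 8.5×25 = 212.5 to 1202.5 (+21%).

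**Sensitivity.** A one-compartment oral steady-state model was run with assumed half-life 4-12 h, absorption rate 0.4-1.5 per h, and the 24-h sample drawn 0.5-3 h after the next dose. For flagged samples under reading (a), AUC rises 23% to 116%, CL/F falls 19% to 54%, and Cmin is multiplied by 2.2 to 11.3. Some samples drawn 0.5 or 1 h after the next dose are not flagged; with C0 missing these add 8% to 29% to AUC.

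**Half-life.** Log-linear regression on 6, 10 and 24 h gives 6.6 h for 70/40/10 and 22.4 h for 70/40/35. The log-slope of the second profile is ln(70/40)/4 = 0.140 per h from 6 to 10 h, and ln(40/35)/14 = 0.0095 per h from 10 to 24 h. That is about a 15-fold break.

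**The case against.** The strongest reply is that the rules are unordered bullets. A pharmacokineticist who discards an invalid 24-h value first would find both ends missing, and Part C would then exclude the profile. That stands as a possible reading. It does not close the point: Part C gives invalid values their own replacement rule and never says that they count as missing, and Part B has no exclusion to fall back on.

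A reader might go further than the documents allow in four ways:

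- **Copying to both ends as a certain result.** It is one of three readings.
- **Badly wrong half-lives.** In Part C the linearity inspection should stop the 22.4 h example, and the positive-slope rule stops more extreme ones. Part B has weaker protection. Half-life is therefore at most a side issue.
- **The pre-dose window makes the pattern more common.** Part C says "The concentrations outside the sampling window will be listed but not used for PK parameter calculation and summary statistics", but not whether such a 0-h value is then treated as missing and filled.
- **Recorded times already settle validity.** Sampling times are used only if available, and the clock time of the next dose is also needed. Neither SAP shows that it is collected. The 10-h comparison is a reasonable proxy without it.

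It is also fair that a true 24-h value above the 10-h value would be unusual, and that with C0 observed the substitution inserts the trough expected at steady state. Individual profiles are to be presented, so a duplicated end value could be noticed. PK is a secondary objective with descriptive summaries, and no efficacy conclusion rests on it.

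**Conclusion.** The point holds as a gap in the derivation rules. For a missing 0-h sample with a 24-h value above the 10-h value, two of the three readings place a presumed post-dose concentration in the profile. In the listed order it sits at both ends, raising AUC0-24 by about 34% to 77% on the illustrative profile, lowering CL/F by 26% to 44%, and raising Cmin no further than the lowest remaining sample, normally the 10-h value. The test also accepts post-dose samples below the 10-h value.

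These sizes rest on assumed concentrations and apply per affected profile. The documents give no basis for how many profiles that is, so no bias in the study means can be stated. The gap is wider in Part B than in Part C. It deserves correction because AUC0-24, Cmin and CL/F are planned outputs, in a study of about 60 subjects that also plans to explore body weight against PK.

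**What to change.** In both SAPs:

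1. Run the validity check before any substitution and set an invalid 24-h value to missing.
2. Where recorded, use the actual sampling time and the time of the next dose: the 24-h sample is invalid if drawn after that dose. Keep the 10-h comparison only as a fallback where those times are lacking and a next-day dose was due. The last condition matters at Part B Flare-up Day 84, since "Subjects not receiving non-flare-up based dosing will only be treated during eligible flare-ups" and some of these subjects may have no dose the next day.
3. Extend the Part C exclusion from both values missing to both missing or invalid, and add it to Part B.
4. Do not estimate lambda-z or half-life from a substituted 24-h value.

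With C0 observed, the 24-h value still takes C0, as now. With C0 missing and the 24-h value invalid, the profile is listed and left out of the parameter calculation.

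The cost is a wording change and a fixed derivation order. A few profiles lose PK parameters, and the timing check helps only where next-dose times were recorded.

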13 APPENDIX

Appendix 1. PROMIS T-Score Conversions

The following conversion tables allow a user to convert Global Physical Health, Global Mental Health, and Total scores into T-scores. T-score distributions are standardized such that a 50 represents the average (mean) for the US general population, and the standard deviation around that mean is 10 points. A high score always represents more of the concept being measured. Thus, a subject who has a T-score of 60 is one standard deviation better (healthier) than the general population.

Table 9: PROMIS T-Score Conversions for Adult Global Physical and Mental Health

Adult Global Physical Health			Adult Global Mental Health		
Raw Score	T-Score	Standard Error	Raw Score	T-Score	Standard Error
4	16.2	4.8	4	21.2	4.6
5	19.9	4.7	5	25.1	4.1
6	23.5	4.5	6	28.4	3.9
7	26.7	4.3	7	31.3	3.7
8	29.6	4.2	8	33.8	3.7
9	32.4	4.2	9	36.3	3.7
10	34.9	4.1	10	38.8	3.6
11	37.4	4.1	11	41.1	3.6
12	39.8	4.1	12	43.5	3.6
13	42.3	4.2	13	45.8	3.6
14	44.9	4.3	14	48.3	3.7
15	47.7	4.4	15	50.8	3.7
16	50.8	4.6	16	53.3	3.7
17	54.1	4.7	17	56	3.8
18	57.7	4.9	18	59	3.9
19	61.9	5.2	19	62.5	4.2
20	67.7	5.9	20	67.6	5.3

Table 10: PROMIS T-Score Conversions for Pediatric Global Health

Pediatric Self-Completed Total			Pediatric Proxy-Completed Total		
Raw Score	T-Score	Standard Error	Raw Score	T-Score	Standard Error
7	16	3.4	7	14.7	2.9
8	17.1	3.6	8	15.3	3.1
9	18.3	3.7	9	16	3.2
10	19.7	3.8	10	16.9	3.4
11	21.2	3.8	11	18.1	3.6
12	22.8	3.7	12	19.4	3.7
13	24.4	3.6	13	21	3.8
14	26.1	3.6	14	22.7	3.8
15	27.6	3.5	15	24.4	3.7
16	29.2	3.5	16	26.1	3.7
17	30.8	3.5	17	27.7	3.7
18	32.4	3.6	18	29.4	3.8
19	34	3.6	19	31.2	3.8
20	35.6	3.6	20	32.9	3.8
21	37.2	3.6	21	34.6	3.8
22	38.8	3.6	22	36.2	3.8
23	40.4	3.6	23	37.9	3.9
24	42.1	3.7	24	39.7	4
25	43.9	3.7	25	41.7	4
26	45.7	3.6	26	43.6	3.9
27	47.5	3.6	27	45.4	3.8
28	49.2	3.6	28	47.3	3.9
29	51.1	3.7	29	49.3	4.1
30	53.3	3.9	30	51.8	4.4
31	55.7	4.2	31	54.5	4.7
32	58.3	4.5	32	57.3	5
33	61.1	4.9	33	60.2	5.4
34	64.2	5.4	34	63.2	6
35	67.5	6.1	35	66.1	6.5

Appendix 2. Flare-up Location Mapping

Table 11: Flare-up Location Mapping

List	Flare Location	Flare Other Specify	Adjusted Location: Combine Left and Right
1	ABDOMEN		Lower spine/abdomen
2	ANTERIOR NECK		Head/Neck
3	CERVICAL SPINE		Cervical spine
4	CHEST		Upper Spine/Chest
5	HEAD		Head/Neck
6	JAW		Jaw
7	LEFT ANKLE OR FOOT		Distal lower extremities
8	LEFT DISTAL LOWER EXTREMITIES		Distal lower extremities
9	LEFT DISTAL LOWER EXTREMITIES		Distal lower extremities
10	LEFT DISTAL UPPER EXTREMITIES		Distal upper extremities
11	LEFT ELBOW		Elbow
12	LEFT HIP		Hip
13	LEFT KNEE		Knee
14	LEFT SHOULDER		Shoulder
15	LEFT WRIST OR HAND		Distal upper extremities
16	LOWER BACK		Lower spine/abdomen
17	LOWER SPINE/ABDOMEN		Lower spine/abdomen
18	LUMBAR SPINE		Lower spine/abdomen
19	NECK		Head/Neck
20	OTHER	ABOVE LEFT KNEE	Knee
21	OTHER	BOTH RIGHT KNEE AND RIGHT HIP	Hip
22	OTHER	LEFT ANTERIOR THIGH	Hip
23	OTHER	LEFT KNEE/ LEFT CALF	Knee
24	OTHER	LEFT NECK	Head/Neck
25	OTHER	LEFT NECK AND SUBMANDIBULAR AREA	Head/Neck
26	OTHER	LEFT POSTERIOR CALF, FOCUS OF TENDERNESS 8 CM BELO	Knee
27	OTHER	LEFT TRICEPS	Shoulder
28	OTHER	NECK (RIGHT AND BELOW THE CLIN)	Head/Neck
29	OTHER	NECK RIGHT AND RIGHT ARM	Shoulder
30	OTHER	RIGHT ARM	Shoulder
31	OTHER	RIGHT BICEP	Shoulder
32	OTHER	RIGHT PECTORAL AND AXILLARY AREA	Upper Spine/Chest
33	OTHER	RIGHT THIGH AND CERVICAL SPINE	Hip
34	OTHER	RIGHT TRICEP	Shoulder

List	Flare Location	Flare Other Specify	Adjusted Location: Combine Left and Right
35	OTHER	UPPER BACK AND RIGHT SCAPULA	Upper back
36	OTHER	LEFT SHOULDER AND LEFT SIDE OF NECK	Shoulder
37	OTHER	RIGHT THIGH	Hip
38	OTHER	RIGHT TRICEPS	Shoulder
39	OTHER	LEFT DISTAL MEDIAL THIGH	Knee
40	OTHER	LEFT SCAPULA	Upper back
41	OTHER	LEFT HAMSTRING	Hip
42	OTHER	LEFT HAMSTRING	Hip
43	OTHER	LEFT FOREARM	Elbow
44	OTHER	LEFT ANTERIOR THIGH	Hip
45	OTHER	LEFT FOREARM	Elbow
46	OTHER	LEFT HAMSTRING	Hip
47	OTHER	RIGHT THIGH, NOT INCLUDING HIP OR KNEE	Hip
48	OTHER	R THIGH	Hip
49	OTHER	RIGHT UPPER THIGH	Hip
50	OTHER	SOURCE ONLY STATED "BACK"	missing
51	OTHER	LEFT CHEEK	Head/Neck
52	OTHER	LEFT ARM	Elbow
53	OTHER	3 SITES: NECK, SKULL, SHOULDER	Head/Neck
54	OTHER	RIGHT GROIN	Hip
55	OTHER	RIGHT CHEEK	Head/Neck
56	OTHER	HEAD, NECK, ARM	Head/Neck
57	OTHER	RIGHT GREAT TOE	Distal lower extremities
58	OTHER	RIGHT LOWER BACK	Lower spine/abdomen
59	OTHER	BICEPS, RIGHT SIDE	Shoulder
60	OTHER	THUMB (RIGHT)	Distal upper extremities
61	OTHER	RIGHT CALF	Knee
62	OTHER	SUBMAXILAR AREA	Jaw
